2.2 Secondary objectives

- Time to symptoms resolution
- Duration of hospitalization
- Overall survival
- Rate of virologic clearance by nasopharyngeal swab at 2 and 4 weeks.
- Evaluation of donor parameters including nasopharyngeal swab positivity and titers levels
- Evaluation of the impact of donor titers level on efficacy.
- Patients' anti-SARS-CoV2 titer assessment pre-infusion for the Treatment group, +2 weeks (+/- 3 days), +4 weeks (+/- 3 days) and +2 months (+/- 5 days). Randomization day will be designated at day 0.

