5.2 Patient procedures and evaluation (see Appendix B)

Patients may be screened, enrolled and randomized remotely. The day of randomization will be designated as day 0 for both Treatment and Control groups. Patients randomized to the treatment arm will need to be seen on the day of infusion which should occur within 48 hours of randomization and be within 96 hours of symptom onset.

5.2.1 Day 0. May be done remotely.

- Screening
- Informed consent must be obtained before performing study related activities (can be from healthcare proxy if subject unable to provide consent due to medical status)
- Baseline Evaluation (at screening)
 1. Demographics (age, sex ethnicity, race)
 2. Medical history
 - a. Date of onset of COVID-19 symptoms
 - b. Date of positive test
 - c. Acute and chronic medical conditions described in the eligibility criteria 3.2.
 - d. Charlson Co-morbidity Index calculation
 3. COVID-19 symptom screen (Y/N)
 - a. Fever (T Max)
 - b. Cough
 - c. Shortness of breath
 - d. Ageusia and/or anosmia
 - e. Myalgias
 - f. Headache
 - g. Other symptoms that the patient attributes to their COVID-19 infection
 4. Documentation of positive nasopharyngeal COVID-19 testing.
 5. Determination of eligibility as per inclusion/exclusion criteria
 6. Randomization

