5.2.2 Plasma infusion day

Patients randomized to the treatment arm will need to be seen on the day of infusion which should occur within 48 hours of randomization and be within 96 hours of symptom onset.

Study plasma administration will be allowed for the Control arm after hospital admission if requested by the patient's medical team.

- On the day of infusion, blood will be drawn for:
 1. Inflammatory markers

- a. D-Dimers
 - b. Ferritin
 - c. CRP
- 2. Serological testing: anti-SARS CoV-2 titers
- 3. Exploratory blood test for genomics (optional)
- 4. Exploratory blood test for cytokines/chemokines (optional)
- 5. Rectal swab for gut microbiome analyses, to be sent to the CDI if possible
- 6. CBC
- 7. Complete chemistry
- 8. ABO Rh

- Procedure:
 - 1. A single unit of approximately 400-500 mL of liquid fresh plasma or 2 units of fresh frozen plasma for a total of approximately 400 mL will be transfused at an approximate rate of 50 mL per hour x 30 minutes, then the rate may be increased up to 150 mL per hour until completion. If plasma availability does not allow for 2 units of FFP, a single unit may be administered.
 - 2. If possible, 10mL of plasma will be collected for research from the infusion line and sent to the CDI
 - 3. The infusion may be slowed or stopped as per investigator's decision for minor transfusion reactions only. The transfusion will be discontinued for any transfusion reactions other than minor allergic reactions.
 - 4. An investigation will be initiated when there are signs of a systemic transfusion reaction.
 - 5. Premedication 30 – 60 minutes prior to the infusion will include 100 mg hydrocortisone IV and may include acetaminophen 650 mg PO and diphenhydramine 25 mg IV. Diphenhydramine 25 mg IV and hydrocortisone 100 mg IV may be repeated as needed for an infusion reaction at the discretion of the investigator.
 - 6. Vitals signs should be monitored following Hackensack Meridian Health Blood and Blood Product Administration SOP guidelines:
 - a. Temperature, pulse, respirations, and blood pressure pre-infusion (within 30 minutes), 15 minutes after the start, every hour during, if a transfusion reaction is suspected or if there is any change in patient condition, post transfusion (5-15 minutes post)

5.2.3 Post enrollment day +3 and day +7 (or closest working day). May be done remotely.

- COVID-19 symptom screen by telephone (Y/N)
 - 1. Fever (T max)
 - 2. Cough
 - 3. Shortness of breath
 - 4. Ageusia and/or anosmia

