8.1 Hypothesis

The primary objective is the hospitalization rate of patients with early COVID-19 infection at high-risk of admission. Suppose the hospitalization rate by 21 days from therapy initiation is 8% for the Treatment group (P_t) and 18% for the Control group (P_c). This phase II design will aim at the following hypothesis:

The design has a type I error rate at 0.05 with statistical power at least 0.80.

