8.3. Analysis Plan

8.3.1 Primary Endpoints

The primary endpoint of the phase II study is the hospitalization rate at 10 days from therapy initiation of patients with early COVID-19 infection at high-risk of admission. The hospitalization rate will be summarized by frequency (%) and compared between the Treatment and Control arms by Mantel-Haenszel test. There will be two interim analyses. Analysis reports will be provided to the DSMB to decide if there is a pronounced treatment effect or futility. A detailed interim analysis plan will be provided before the start of the interim analysis.

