8.3.3 Secondary Endpoints

- Time to Symptoms Resolution

Kaplan-Meier analysis will be used to describe time to symptoms resolution and the median time with 95% CI will be reported. Log-rank test will be utilized to compare the time to symptoms resolution between the Treatment and Control arms.

The time to symptoms resolution is defined as the time in days from therapies initiation to the first documented symptoms resolution as assessed by a local site. Patients whose symptoms are not resolved, or result in death, or lost follow-up on the designed follow-up date, will be censored on that date.

- Overall Survival (OS)

Overall survival (OS) will be defined as the time in days from study entry to death. Patients who are alive on the date of closing follow-up will be censored on that date. All events of death will be included, regardless of whether the event occurred while the subject was still taking new therapies, or after the subject discontinued study therapy. If a subject has not died, then the data will be censored according to the following rule: if the subject was lost to follow-up, then data will be censored at the last study visit, or the last contact date, or the date the subject was last known to be alive, whichever is later. If the subject was not lost to follow-up, then data will be censored at the last study visit or the last contact date, whichever is later.

OS will be estimated by Kaplan-Meier methodology, and median OS with 95% CI will be reported. And the OS between the Treatment and Control arms will be compared by Log-rank test.

- Rate of Virologic Clearance

The rate of virologic clearance by nasopharyngeal swab at 2 weeks and 4 weeks will be summarized by frequency (%) and compared between two randomized arms by Mantel-Haenszel test. The marginal model will be fitted to the rate of virologic clearance at different time points to evaluate the main effect of randomized arms by using the generalized estimating equations method.

Viral clearance at a designed follow-up date is defined as the cycle threshold (Ct) of RT-PCT at that designed follow-up date 40.

- Evaluation of Donor parameters

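### The primary endpoint and time to symptom resolution start at therapy initiation, a date Control does not have before admission and Treatment reaches up to 48 hours after day 0

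*Combined protocol and SAP*

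**What the plan says.** - **Primary endpoint.** Section 8.3.1 uses the "hospitalization rate at 10 days from therapy initiation", "compared between the Treatment and Control arms by Mantel-Haenszel test". Section 8.1 sets the design rates, 8% v 18%, for "the hospitalization rate by 21 days from therapy initiation".
- **Symptoms.** Section 8.3.3 defines time to symptom resolution as "the time in days from therapies initiation to the first documented symptoms resolution".
- **Survival.** The same section uses a different origin: "Overall survival (OS) will be defined as the time in days from study entry to death".
- **Day 0.** Section 5.2: "The day of randomization will be designated as day 0 for both Treatment and Control groups". Section 2.2 agrees: "Randomization day will be designated at day 0".
- **Infusion.** Section 5.2.2 says that it "should occur within 48 hours of randomization and be within 96 hours of symptom onset".
- **Control.** Sections 4.1, 5.2.2 and 5.2.5 give Control best supportive care, with study plasma available only once the patient is hospitalized.

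No section equates therapy initiation with randomization, gives Control a start date, or says how Treatment patients admitted before infusion or never infused enter the primary comparison.

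**The concern.** A primary endpoint needs a time origin that exists for every patient and means the same thing in both arms. Here the only dated study therapy a Control patient can receive follows admission, which is the event being counted. In Treatment the origin is the infusion, which some patients may never reach. Section 3.2 admits patients up to 96 hours from onset and infusion must also fall within 96 hours of onset, so a patient randomized at hour 90 has 96 − 90 = 6 hours left.

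An analyst must therefore choose a Control origin and a Treatment denominator that the plan does not state. If Control is counted from day 0, two asymmetries follow:

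- The Treatment window opens and closes up to 2 days later.
- A symptom resolution on the same calendar day is scored up to 2 days shorter in Treatment, and a resolution before infusion has no valid time at all.

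The same endpoint drives the stopping decisions at 102 and 204 patients, so the choice would affect the interim looks as well as the final analysis. Overall survival and the scheduled swab results are not affected.

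**Working it through.** **1. Reproduce the design.** Inputs from 8.1 and 8.2: 8% v 18%; one-sided alpha 0.05; power at least 0.80; 51, 102 and 153 per arm; reject at Z ≤ −2.84929, −2.01475, −1.64504; accept H0 at Z ≥ 0.17929, −0.94399 (taken as binding). Simulating 1,000,000 binomial trials with a pooled Z gives type I error 0.050 at 18% v 18% and power 0.81 at 8% v 18% (0.79 to 0.80 by normal approximation). N=306 reproduces. The pooled Z stands in for the Mantel-Haenszel test because the mix of Charlson strata is not given.

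**2. Assumptions, none from the documents.** Admission timing from randomization is F(t) = 1 − exp(−λt^k) with F(W) = 0.18. W is 10 or 21 days; k = 1.5 (rising), 1 (constant) or 0.6 (front-loaded). Infusion delay d is 0, 1 or 2 days with weights w. Control is counted from randomization to day W.

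**3. Treatment rate when there is no true effect.**

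- Shifted window, all kept: Σ w F(W+d)
- Shifted window, infused only: Σ w [F(W+d) − F(d)] / Σ w [1 − F(d)]
- Pre-infusion admissions dropped, both arms closing on day W: (0.18 − e)/(1 − e), with e = Σ w F(d)

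Example (constant, 10 days, delay in thirds): λ = −ln(0.82)/10 = 0.0198, F(1) = 0.0197, F(2) = 0.0389, so e = (0 + 0.0197 + 0.0389)/3 = 0.0195. All kept: (0.180 + 0.196 + 0.212)/3 = 0.196. Dropped: (0.18 − 0.0195)/(1 − 0.0195) = 0.164.

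**4. Delay in thirds.** This is a high-delay case: a 2-day delay requires randomization within 96 − 48 = 48 hours of onset. Cells show the Treatment rate, then one-sided type I error against 18%.

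| Timing, window | e | Shifted, all kept | Shifted, infused only | Dropped, common close |
|---|---|---|---|---|
| Rising, 10 d | 0.79% | 20.5%, 0.015 | 19.8%, 0.021 | 17.3%, 0.066 |
| Rising, 21 d | 0.26% | 19.2%, 0.029 | 19.0%, 0.032 | 17.8%, 0.055 |
| Constant, 10 d | 1.95% | 19.6%, 0.024 | 18.0%, 0.050 | 16.4%, 0.10 |
| Constant, 21 d | 0.94% | 18.8%, 0.035 | 18.0%, 0.050 | 17.2%, 0.07 |
| Front-loaded, 10 d | 4.05% | 18.9%, 0.032 | 15.5%, 0.14 | 14.5%, 0.19 |
| Front-loaded, 21 d | 2.62% | 18.5%, 0.041 | 16.3%, 0.10 | 15.8%, 0.12 |

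With a true 8% v 18% and all patients kept in the shifted window, power is 0.69 to 0.70 (rising), 0.73 to 0.74 (constant) and 0.76 to 0.77 (front-loaded) at 10 days. At 21 days it is 0.75 to 0.76, 0.77 to 0.78 and 0.78 to 0.79.

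**5. Mostly same-day infusion (80% day 0, 20% next day).** Across all three timings and both windows, a shifted window gives type I error 0.040 to 0.065. Power with all kept is 0.79 to 0.80.

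**6. Symptoms.** If Control runs from day 0, the recorded Treatment time is the true time minus d, with 0 ≤ d ≤ 2 days, so the comparison leans toward plasma. I attach no error rate: it depends on the resolution-time distribution and on whether resolution is dated to the visit or to the day it occurred.

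**7. Power once the origin is randomization.** If 8% and 18% are all-randomized rates from day 0, step 1 stands. Otherwise:

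- *8% applies only after infusion, delay in thirds.* Control hazard applies before infusion and is multiplied by ln(0.92)/ln(0.82) = 0.42 afterwards. Constant timing gives Treatment rates of 9.05% (10 d) and 8.50% (21 d), with power about 0.71 and 0.76. Rising gives about 0.77 and 0.80; front-loaded about 0.60 and 0.68.
- *Share u uninfused at the Control rate.* The Treatment rate is 0.08(1 − u) + 0.18u. For u = 5, 10 and 20% it is 8.5, 9.0 and 10.0%, with power about 0.76, 0.71 and 0.61.

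**The case against.** The best defence is that therapy initiation is loose wording for day 0. Section 5.2 fixes day 0 for both groups, 8.3.2 attaches day 0 to the infusion, and section 8 speaks of therapies in the plural, so supportive care might be taken to start at randomization. A statistician could default to 5.2. This is plausible, but no section says it. Even if it is accepted for Control, a Treatment patient infused up to 48 hours later, or never, still has a different origin or none.

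The second defence is size, and it largely stands. With mostly same-day infusion, error and power barely move, and no section tells the analyst to drop anyone.

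Three stronger readings are tempting and are not supported:

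- *That the rule biases the primary result toward plasma.* Section 1.4 places most admissions in the second week of disease, and 3.3 excludes patients who need oxygen. Both suggest admissions rising after day 0, and a later-closing Treatment window then works against plasma.
- *That error inflates only if admissions are front-loaded.* Dropping pre-infusion admissions under a constant hazard also gives about 0.10 at 10 days.
- *That moving to randomization recovers power.* If 8% holds only after infusion, power can be as low as about 0.60.

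The conflict between 10 and 21 days is a separate matter. It enters here only because the endpoint has to be rewritten with one length.

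**Conclusion.** The point holds as a defect of definition. The primary endpoint and time to symptom resolution have no stated origin in Control and none for uninfused Treatment patients, and the likeliest reading gives the arms different origins. Confidence in that is high, because it rests on the text alone.

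Confidence in the size of the bias is low. Admission timing, infusion delay and uninfused share are all assumed. The shifted window runs from negligible with mostly same-day infusion, to conservative with rising admissions and long delays (type I error down to 0.015), to inflated with front-loaded admissions, long delays and an infused-only analysis (0.10 to 0.14). Dropping pre-infusion admissions with delay in thirds gives about 0.055 to 0.066 (rising), 0.07 to 0.10 (constant) and 0.12 to 0.19 (front-loaded). A reader might infer that the trial's error control has failed; the documents do not show that. This should be fixed, but it does not invalidate the design.

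**What to change.** In 8.1, 8.3.1 and 8.3.3:

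- Define time zero as randomization (day 0) in both arms.
- Define the primary endpoint as the proportion of all randomized patients, by assigned arm, admitted from randomization through one stated day. Sections 8.1 and 8.3.1 must agree on that day.
- Count an admission before or without infusion as an event in the assigned arm.
- Measure time to symptom resolution from randomization, keeping patients whose symptoms resolve before infusion.
- State that 8% v 18% are all-randomized rates from randomization over the chosen window, and what uninfused share they allow for.

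This changes wording only. N=306 and alpha 0.05 are untouched, and power of about 0.80 stands if the rates are read that way. The cost is candour about power. If 8% applies only after infusion, stated power falls to about 0.60 to 0.80 (delay in thirds); if 5, 10 or 20% go uninfused at the Control rate, it is about 0.76, 0.71 or 0.61. I would restate the power on the chosen basis rather than enrol more patients. The reason for the change is an origin that exists in both arms, not a gain in power.

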7.3 Data Safety Monitoring Board (DSMB)

This study will be approved and monitored by the HackensackUMC DSMB. The DSMB is responsible for the monitoring of investigator initiated research studies to ensure the safety of participants, the integrity of the data, and the appropriate termination of studies in the event that undue risks have been uncovered, or it appears that trials cannot be conducted successfully. The DSMB provides multidisciplinary, independent oversight of research studies conducted by HackensackUMC staff and or affiliates. The DSMB can require protocol modifications related to participant safety and to recommend suspension or termination to the IRB and institutional official of any research protocols that fall within its jurisdiction. The DSMB may request that HackensackUMC's Corporate Compliance Department conduct periodic audits to assure that data are being collected and recorded according to the protocol.

The investigator is required to submit monthly monitoring reports which include current enrollment data, adverse event summary data and any other data requested by the DSMB. The DSMB will meet monthly to review the trial progress, adverse event data, and any relevant information such as significant amendments or reviews from IRB submitted by the principal investigator. If significant concerns are raised by the DSMB, the concerns will be forwarded to the PI as well as recommendations made to the IRB, and Institutional Official. Recommendations may include modifying, suspending, or terminating the protocol.

8. Study Design and Sample Size Considerations

This is a randomized phase II trial to assess the efficacy and safety of treatment with convalescent plasma infusion (Treatment) versus without convalescent plasma infusion (Control) in patients with early COVID-19 infection at high-risk of admission. Eligible subjects will be stratified randomized by their Charlson Comorbidity Index scoring in a 1:1 ratio to receive either Treatment or Control (8.4). For this trial, we have considered a group sequential design which has more interim analyses and utilized a three-stage O'Brien-Fleming design.²³

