8.2 Study design

This trial will follow a one-sided three-stage O'Brien-Fleming design as follows.²³

The first stage analysis will be after 51 subjects in each arm, that is after a total of 102 subjects. If the Z statistic is greater than or equal to 0.179 (p-value ≥ 0.571), the hypothesis H_0 is accepted and the trial stops, we conclude the Treatment is not worth pursuing; if the Z statistic is less than or equal to -2.849 (p-value ≤ 0.002), the hypothesis H_0 is rejected and early evidence for promising efficacy is established. Otherwise, the trial continues to the next stage.

The second stage analysis will be after 102 subjects in each arm, that is after a total of 204 subjects. If the Z statistic is greater than or equal to -0.944 (p-value ≥ 0.173), the hypothesis H_0 is accepted and the trial stops, we conclude the Treatment is not worth pursuing; and if the Z statistic is less than or equal to -2.015 (p-value ≤ 0.022), the hypothesis H_0 is rejected and early evidence for promising efficacy is established. Otherwise, the trial continues to the final stage.

At the final stage, a total of 306 subjects will be recruit and 153 of them for each arm. The hypothesis H_0 is rejected for efficacy if the Z statistic is less than -1.64504 (p-value < 0.4498). Otherwise, the H_0 is not rejected.

Stage	Cumulative total sample size N	Cumulative sample size for treatment group N(Grp 1)	Cumulative sample size for control group N(Grp 2)	Evidence for undesired rate if Z statistic \geq (Accept H_0 if Z-statistic \geq)	Evidence for desired rate if Z statistic \leq (Reject H_0 if Z-statistic \leq)	Evidence for undesired rate if p-value \geq (Accept H_0 if p-value \geq)	Evidence for desired rate if p-value \leq (Reject H_0 if p-value \leq)
1	102	51	51	0.17929	-2.84929	0.57115	0.00219
2	204	102	102	-0.94399	-2.01475	0.17259	0.02197
3	306	153	153	-1.64504	-1.64504	0.04998	0.04998

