8.4 Charlson Co-morbidity Index22

Patients will be stratified in 4 groups based on their Charlson Co-morbidity Index scoring:

Low score ≤ 3 points; moderate score = 4, 5 points; high score = 6, 7 points; very high score ≥ 8 points.

One Point for each:

- Myocardial infarction (history, not ECG changes only)
- Congestive heart failure
- Peripheral disease (includes aortic aneurysm ≥ 6 cm)
- Cerebrovascular disease: CVA with mild or no residua or TIA
- Dementia
- Chronic pulmonary disease
- Connective tissue disease
- Peptic ulcer disease
- Mild liver disease (without portal hypertension, includes chronic hepatitis)
- Diabetes without end-organ damage (excludes diet-controlled alone)

Two Points for each:

- Hemiplegia
- Moderate or severe renal disease
- Diabetes with end-organ damage (retinopathy, neuropathy, nephropathy, or brittle diabetes)
- Tumor without metastasis (exclude if ≥ 5 y from diagnosis)
- Leukemia (acute or chronic)
- Lymphoma

Three Points for each:

- Moderate or severe liver disease

Six Points for each:

- Metastatic solid tumor
- AIDS (not just HIV positive)

<https://www.mdcalc.com/charlson-comorbidity-index-cci>

9. Regulatory consideration

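### Randomization is stratified by four Charlson groups, but no analysis uses them; an unstratified primary test would be conservative and lose some power if Charlson group predicts admission

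*Combined protocol and SAP*

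**What the plan says.** The opening of section 8 (repeated in the Protocol Summary) states: "Eligible subjects will be stratified randomized by their Charlson Comorbidity Index scoring in a 1:1 ratio". Section 8.4 gives the cut points (3 or less, 4-5, 6-7, 8 or more) and says "Patients will be stratified in 4 groups based on their Charlson Co-morbidity Index scoring". Section 5.2.1 lists "Charlson Co-morbidity Index calculation" in the baseline evaluation, ahead of randomization.

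The analysis sections do not mention these groups:

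- **Primary endpoint (8.3.1):** the hospitalization rate is "compared between the Treatment and Control arms by Mantel-Haenszel test". No stratifier is named.
- **Virologic clearance (8.3.3):** "compared between two randomized arms by Mantel-Haenszel test", followed by a marginal model for the main effect of arm.
- **Time to symptom resolution and overall survival (8.3.3):** log-rank tests that name the two arms only.
- **Logistic and mixed models (8.3.3):** no Charlson term.

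Section 8.2 compares an otherwise undefined Z statistic with accept and reject boundaries at three looks. On further detail, 8.3.1 says: "A detailed interim analysis plan will be provided before the start of the interim analysis".

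**The concern.** Randomizing within strata makes the arms more alike on Charlson group than chance would. If Charlson group predicts admission, the difference between arms varies less than an unstratified variance formula assumes. The unstratified Z is then too small in absolute size, so the test rejects less often than its nominal 5% under the null and loses power under the alternative.

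The test name does not settle which version is meant. Mantel-Haenszel usually implies strata, but 8.3.3 uses it for donor parameters and 8.3.4 for univariate associations, with no strata described in either place. The stratified and unstratified Z can also fall on opposite sides of a boundary on the same data, so leaving the choice open leaves room to make it after data are seen.

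**Working it through.** **Inputs from the plan.** Control 18% and Treatment 8% (8.1, taken as they stand); one-sided type I error 0.05 and power at least 0.80 (8.1); looks at 102, 204 and 306 patients (8.2). Reject at Z ≤ -2.84929, -2.01475, -1.64504; accept H0 at Z ≥ 0.17929, -0.94399 (8.2 table).

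**Assumed, because the plan gives none of these.** The share of patients in each Charlson group, the gradient in admission risk (an odds ratio, OR, per Charlson step), a common treatment OR giving 8% overall, and permuted blocks of 4 within strata.

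**Step 1: reproduce the plan's own figure.** The drift at 153 per arm is 0.10 / √[(0.08×0.92 + 0.18×0.82)/153] = 0.10 / √(0.2212/153) = 2.630. Passing this through the three-stage boundaries gives type I error 0.050 and power 0.802 (0.794 with a pooled variance). The stated design reproduces.

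**Step 2: the two statistics.** The unstratified Z uses a pooled variance based on p(1-p). The stratified statistic is

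Z = Σ(a_k - n_1k m_k/N_k) / √[Σ n_1k n_0k m_k(N_k - m_k) / (N_k²(N_k - 1))],

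where, in Charlson group k, a_k is Treatment admissions, m_k all admissions, n_1k and n_0k the arm sizes and N_k their sum. Negative values favour Treatment, as in 8.2.

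**Step 3: hand check of the conservatism.** Take a mix of 60/25/10/5% (lowest to highest group) and OR 2 per step, so Control rates are 11.5/20.6/34.2/50.9%.

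- Within-group variance: 0.60×0.115×0.885 + 0.25×0.206×0.794 + 0.10×0.342×0.658 + 0.05×0.509×0.491 = 0.137.
- Overall variance: 0.18×0.82 = 0.1476. The ratio is 0.928, so the unstratified Z has a standard deviation of about √0.928 = 0.963.
- At the final critical value: 1.64504/0.963 = 1.708, a one-sided tail of about 0.044 instead of 0.050.

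**Step 4: three-stage simulation** (200,000 trials per setting; U = unstratified, S = stratified).

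| Mix, % | OR per step | Alpha U / S | Power U / S |
|---|---|---|---|
| 60/25/10/5 | 1 | 0.0508 / 0.0502 | 0.8085 / 0.8067 |
| 60/25/10/5 | 2 | 0.0446 / 0.0501 | 0.8168 / 0.8264 |
| 60/25/10/5 | 3 | 0.0352 / 0.0502 | 0.8309 / 0.8604 |
| 85/9/4/2 | 1.5 | 0.0498 / 0.0502 | 0.8077 / 0.8077 |
| 85/9/4/2 | 3 | 0.0414 / 0.0501 | 0.8214 / 0.8442 |
| 70/10/10/10 | 3 | 0.0282 / 0.0497 | 0.8442 / 0.8835 |

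The 0.0446 in the second row agrees with the hand check. Across eight mixes (those above and 25/25/25/25, 40/30/20/10, 70/15/10/5, 60/15/10/15, 95/3/1/1):

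| OR per step | Alpha U | Alpha S | Power change from stratifying, points |
|---|---|---|---|
| 1 | 0.050-0.051 | 0.049-0.051 | -0.1 to -0.4 |
| 1.5 | 0.047-0.050 | 0.049-0.050 | -0.4 to +0.4 |
| 2 | 0.040-0.049 | 0.049-0.051 | -0.1 to +1.6 |
| 3 | 0.027-0.047 | 0.050-0.051 | +1.0 to +3.9 |

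The lowest stratified power was 0.8033 (95/3/1/1, OR 1). A separate simulation (40/30/20/10, 60,000 trials) gave alpha 0.044 vs 0.051 and power 0.816 vs 0.827 at OR 2, and 0.035 vs 0.052 and 0.829 vs 0.857 at OR 3. Replacing the common OR by a constant risk ratio of 8/18 (three mixes, OR 1.5-3) gave -0.1 to +2.3 points.

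**Step 5: how often the choice changes the decision.** With true rates of 8% and 18%, the two Z values gave a different stopping look or conclusion in 1.7-5.4% of trials at OR 1 and 9.4-19.0% at OR 3. The conclusion itself differed in 0.3-1.4% and 2.1-4.3%.

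**Step 6: secondary tests, on inputs that are entirely assumed.**

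- Symptom-resolution log-rank (306 patients, median 10 days, treatment hazard ratio 1.4, two-sided 0.05): stratifying changes power by -0.4 points with no gradient, +0.9 to +6.8 at a hazard ratio of 1.5 per step, and +3.5 to +19.9 at 2 per step.
- Virologic clearance (50% vs 66%): -0.3 points with no gradient, +0.8 to +5.2 at OR 2-3 per step.
- Overall survival was not quantified.

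**The case against.** **A stratified test is the natural reading.** Mantel-Haenszel is the standard way to combine 2×2 tables across strata, and section 8 points to the four groups of 8.4. This may well be the intent, in which case no power is lost and only a sentence is missing. But the name is also used where no strata are described, and the two log-rank tests as written are unstratified.

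**The interim analysis plan could define Z.** Because 8.2 applies one Z to all three looks, defining it for the interims would in practice fix the final look too. That is reasonable, but as described the later plan covers neither the final analysis nor the secondary tests.

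**The larger gains need unlikely inputs.** This stands. In the list printed in 8.4, age, BMI and hypertension score nothing, yet in 3.2 age 65 or over, BMI 30 or above, or hypertension alone is enough to qualify. The lowest group may therefore dominate. With 85-95% of patients there and OR 1.5 or less, stratifying changes power by 0 to -0.4 points. The +3.9 points needs a 27-fold odds range across groups (3³). The +19.9 points for the log-rank needs an eightfold hazard range (2³).

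**Conservatism depends on balance within strata.** This also stands, since no block method or size is given. Without such balance, unstratified alpha stays at 0.049-0.051. The change from stratifying is then -0.6 to +4.5 points, with stratified power of about 0.799-0.801 at OR 1.

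**Differing decisions are not harm in themselves.** Any two valid statistics sometimes straddle a boundary. Step 5 supports fixing the choice in advance; the case for the stratified version rests on steps 3 and 4.

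**Conclusion.** The point holds, as an item to consider. The randomization strata appear in no analysis, and the text does not settle whether the primary test is stratified. If it is run unstratified, with arms balanced within groups and Charlson group prognostic, it is conservative and gives up power: at most 1.6 points at OR 2 per step, and 1.0 to 3.9 points at OR 3. At OR 1.5 or less the difference is negligible in either direction. Type I error is not materially inflated, and power stays above 0.80 in every stratified-randomization setting tried.

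The sizes are illustrative, not bounds, because the plan gives no group shares, group-specific admission rates or block size. The secondary-test figures are weaker still, since their event rates and treatment effects are assumed too.

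**What to change.** Add one sentence to 8.3.1: the Z compared with the 8.2 boundaries, at both interims and at the final analysis, is the signed one-sided Cochran-Mantel-Haenszel Z (Treatment minus Control), stratified by the four Charlson groups of 8.4 as recorded at randomization. The sentence could sit in the interim analysis plan instead, provided it is written before the first interim and also covers the final analysis.

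Use the same strata for the virologic-clearance Mantel-Haenszel test and both log-rank tests. A stratum with patients in only one arm contributes zero, so merging sparse groups is not needed for validity. Any merging should be fixed in advance, without reference to outcomes by arm. The marginal model for virologic clearance can stay as written: adding stratum terms risks separation and, with a logit link, would change the estimate to a conditional effect. A stratum term in the mixed model for titers is optional.

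The cost is wording only, since the index is already calculated before randomization. If Charlson group turns out not to be prognostic, the price on the primary test is about 0.2 points of power, or up to 0.4 if 95% of patients fall in the lowest group.
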